Patients will be randomized to either sham video headset group or video headset analgesia group. Study coordinators will be assigned to either randomize and program headsets, or to assess patients' during sessions. All enrolled patients will receive education by research team who will demonstrate how to adjust the headset strap, activate the device, and adjust the volume following a predetermined script with the goal of making patients feel comfortable using the device on their own. Patients will be assured they will receive the routine pain control in addition to video headset experience.

Anesthetic management will follow pre-established clinical and institutional guidelines. Anesthesia will be at attending anesthesiologist's discretion; usually that will be spinal anesthesia without intrathecal opioids. Intraoperative and postoperative opioids will also be given at the discretion of the attending anesthesiologist. Prophylactic antibiotics will be given per surgical routine. Other intraoperative and postoperative medications may be used and include anti-inflammatory medications, gabapentin, pregabalin, ketamine, or lidocaine patches. Clinicians will be encouraged to give a single dose of dexamethasone (4-8 mg) for PONV prophylaxis. Inhaled steroids will be permitted as necessary to treat reactive airway disease.

Patients will be randomized in a 1:1 ratio to either relaxation program the morning of the first postoperative day, before start the intervention. Randomization will be based on computer-generated codes with random blocking and no stratification. Allocation will be concealed by a web-based system. The use of the video headset will be offered postoperatively while patients are awake between 8 AM to 4 PM. **Each session will have a maximum duration of 8 minutes. We will target 3 session per day, with at least one hour separating each treatments.** Treatments will continue for two postoperative days or until hospital discharge, whichever comes first.

The study device is a Pico G2 4K headset, but all labels will be masked to reduce

Virtual Reality Distraction for Reduction in Acute Postoperative Pain

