4. **Post discharge pain outcomes.** Patients will be called one week after hospital discharge to assess post discharge pain outcomes using a validated questionnaire (Pain Outcomes Questionnaire Short Form¹⁴) which evaluates five domains (pain, mobility, activities of daily living, vitality, negative affect and fear). The Pain Outcomes Questionnaire Short Form is scored from 0 to 190 and higher scores are related with worst pain outcomes.

Tertiary Outcomes

1. **Anti-emetic medications.** We will record use of anti-emetic medications, and the outcome variable will be calculated as the number of anti-emetic medications administered starting at the first pre-intervention pain score measurement, POD1, until end of postoperative day two or hospital discharge, whichever occurs first.
2. **Patient mobility score.** We will measure patient mobility using physical therapy daily postoperative assessment (“6 Clicks” Basic Mobility Inpatient Short Form questionnaire¹⁵) starting at the first pre-intervention pain score measurement, POD1, until end of postoperative two or hospital discharge, whichever occurs first. The “6 Clicks” Basic Mobility Inpatient Short Form questionnaire is scored from 6 to 24 and higher scores are related with lower levels of functional impairment.

F. Data Analysis

We will assess the balance between randomized groups on baseline variables using the standardized difference (i.e., difference in means or proportions divided by the pooled standard deviation). For all analyses we will adjust for baseline variables having absolute standardized difference <0.10 ¹⁶. The analyses will be carried out using a modified Intention-to-Treat approach. More specifically, all patients who receive the treatment for

Virtual Reality Distraction for Reduction in Acute Postoperative Pain

any duration of time will be included in the analysis. For example, if a patient chose to withdraw on POD 2, their measurements from POD1 would still be used in the analysis. We'll only exclude patients who didn't receive any treatment at all either due to refusal or because they chose to withdraw.

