Primary outcome. We will assess the effect of VR on NRS pain score after each study treatment over postoperative days one and two using a linear mixed effects model on the series of post-VR pain scores while adjusting for the corresponding pre-VR pain score, with time and randomized group as fixed effect categorical variables. We will adjust for within-subject correlation across the pain scores using either an autoregressive AR (1) or unstructured correlation matrix, whichever has better fit (lower AIC, BIC). We will assess the group-by-time interaction, but even if significant ($P < 0.15$) the primary result will be made collapsing over time.

Secondary Outcomes

1. **Total opioid consumption.** We will assess the effect of VR on log-transformed total opioid consumption starting at the first pre-intervention pain score measurement, POD1, and until end of postoperative day 2 or hospital discharge, whichever occurs first, using a linear regression model.
2. **Pain scores.** We will assess the effect of VR on pain score over time starting at the first pre-intervention pain score measurement, POD1, and until end of postoperative day 2 or hospital discharge, whichever occurs first, using a linear mixed effects regression to account for within-subject correlation. Only the pain scores from routine nurse assessments will be used here (pain scores from Aim 1 won't be used).
3. **Perception of video system usability.** We will assess the effect of VR on perception of video system usability as measured by the System Usability Scale using a Wilcoxon rank-sum test and report the median difference (along with the 95% CI) estimated using the Hodges-Lehmann approach.
4. **Post discharge analgesia.** We will assess the effect of VR on analgesia scores one week after discharge using a Wilcoxon rank-sum test and report the median

Virtual Reality Distraction for Reduction in Acute Postoperative Pain

difference (along with the 95% CI) estimated using the Hodges-Lehmann approach.

Tertiary Outcomes

5. **Anti-emetic medications.** We will assess the effects of VR on the number of times a patient required anti-emetic medication within starting at the first pre-intervention pain score measurement, POD1, and until postoperative day 2 or hospital discharge, whichever occurs first, using a Wilcoxon rank-sum test, and report the median difference (along with the 95% CI) estimated using the Hodges-Lehmann approach.

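### The opioid and nurse-pain models name no baseline covariate; the balance rule that could supply one leaves entry to chance and, as printed, inflates type I error

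*Combined protocol and SAP*

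**What the plan says.** Section 3.F (Data Analysis) fixes a covariate for the primary model only, which is fitted while "adjusting for the corresponding pre-VR pain score".

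For secondary outcome 1 it says "We will assess the effect of VR on log-transformed total opioid consumption starting at the first pre-intervention pain score measurement, POD1", by linear regression. Secondary outcome 2 is analysed "using a linear mixed effects regression to account for within-subject correlation", and "Only the pain scores from routine nurse assessments will be used here". Neither entry names a baseline covariate.

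Section 3.E (Measurements) lists PACU and ward opioid consumption, and pain before surgery, in PACU and on the ward, as day-of-surgery baseline data. Section 3.D (Protocol) says "Patients will be randomized in a 1:1 ratio to either relaxation program the morning of the first postoperative day", without stratification. The day-of-surgery values therefore precede randomization and are valid covariates.

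Their only route into the two models is the general rule that opens section 3.F: "For all analyses we will adjust for baseline variables having absolute standardized difference <0.10".

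**The concern.** The rule selects covariates by the balance observed in the trial, not by how well they predict the outcome. Chance therefore decides which model is fitted. Read literally, it adjusts where the arms already agree and leaves the covariate out where they differ, which is where adjustment does most for the validity of the test.

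Average pain and opioid consumption are the two secondary hypotheses in section 2, and section 1.1.E justifies the trial partly because earlier VR studies did not evaluate opioid use. At stake are the error rate of those two tests and some of the precision that data already collected would give.

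**Working it through.** **1. The plan's own figures.** With a 1-point difference, SD 1.5, two-sided 0.05 and 90% power, a t-test needs 49 per group (power 0.904; 48 gives 0.898), matching the stated 98. A four-look design with gamma -4 for efficacy and -1 for non-binding futility inflates this by 1.130: 98 × 1.130 = 110.7, close to the stated 113. Cumulative efficacy probabilities come out at 0.076, 0.359, 0.712 and 0.900, against the stated 0.08, 0.36, 0.71 and 0.90. The sample size is not in question. It concerns the primary outcome; the plan computes no power for these two models.

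**2. Chance of entry.** Under 1:1 randomization the standardized difference d of a baseline variable has standard error √(4/N). At N = 113, P(|d| < 0.10) = 2Φ(0.10/√(4/113)) − 1 = 0.405. A given variable enters in about 40% of trials as printed, and in about 60% if the inequality is reversed.

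**3. Type I error, one baseline.** Let r be the correlation of baseline with outcome (assumed) and u = d/√(4/N). Under the null the unadjusted statistic given u is approximately normal with mean ru and variance 1 − r². The adjusted test has 5% error whatever u is. Integrating over u:

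| | r = 0.3 | r = 0.5 | r = 0.6 |
|---|---|---|---|
| Unadjusted error when \|d\| < 0.10 | 4.08% | 2.58% | 1.68% |
| Unadjusted error when \|d\| > 0.10 | 5.62% | 6.65% | 7.26% |
| Rule as printed: 0.405 × 5% + 0.595 × second row | 5.4% | 6.0% | 6.3% |
| Rule reversed: 0.405 × first row + 0.595 × 5% | 4.6% | 4.0% | 3.7% |

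Simulation agrees (printed 5.3%, 6.0%, 6.3%; reversed 4.5%, 4.0%, 3.6%), and gives 4.9% to 5.0% when the covariate is always included. In the 11% of trials with |d| > 0.30 the printed rule omits the covariate, and the error is 8%, 14% and 18%.

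**4. Opioid power, one baseline.** Section 2's 25% reduction is ln 0.75 = −0.288. Assume a log-SD of 0.7 and no zero totals. With fixed adjustment, power = Φ(0.288/(0.7 × √(1 − r²) × √(4/113)) − 1.96), which is 59% at r = 0 and 71% at r = 0.5. Simulated t-test values are slightly lower:

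| | r = 0.3 | r = 0.5 | r = 0.6 |
|---|---|---|---|
| No covariate | 58% | 58% | 58% |
| Rule as printed | 59% | 63% | 65% |
| Rule reversed | 60% | 66% | 70% |
| Always adjusted | 62% | 70% | 77% |

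At log-SD 0.8 and r = 0.5 the four rows are 47%, 52%, 54% and 58%.

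**5. Several baselines.** The rule covers every baseline variable, and section 3.E lists several that may predict opioid use. With four, pairwise correlation assumed 0.5 or 0.7, N = 113 and log-SD 0.7, simulation gives:

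| Each r with outcome | Type I, printed | Type I, reversed | Power, printed | Power, reversed | Power, one fixed covariate |
|---|---|---|---|---|---|
| 0.3 | about 6% | about 5% | 61–63% | 62–63% | 62% |
| 0.5 | 7–8% | about 5% | 68–70% | 71–75% | 70–71% |

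The power gap against one fixed covariate closes or reverses. The type I error of the printed rule gets worse.

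**6. Nurse pain.** For 1 point, r = 0.5 and N = 113, taking one summary per patient: at SD 1.5 (borrowed from the session scores), power is 95% printed, 97% reversed and 98% always adjusted. At an assumed SD of 2.0 it is 79%, 83% and 86%.

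**The case against.** **The one-covariate simulation overstates the loss of power.** This stands. Step 5 shows that several correlated baselines can bring the rule level with one fixed covariate, or above it when reversed. A reader might infer from step 4 alone that the rule must cost several points of power; the documents do not support that.

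**The inequality is probably a misprint.** The rule follows a sentence about assessing balance, so the opposite sign is plausible. Correcting it would remove the inflation. It would still leave entry to chance, and with one prognostic baseline the test would be conservative and less powerful than fixed adjustment.

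**Power is lost only against a preferred model.** Also true: both readings gain power over no adjustment. Nor does the plan contradict itself. It claims sufficiency for moderate effects in most other outcomes, and a 25% reduction is 0.288/0.8 to 0.288/0.7, or 0.36 to 0.41 SD, at the assumed SDs of 0.8 and 0.7.

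**The inputs are assumed.** The documents give no log-SD, nurse-pain SD or baseline correlation. At r = 0.3 the gain is only about 1.5 to 2 points. Residual block ("usually that will be spinal anesthesia without intrathecal opioids") and varying length of stay could weaken the correlation, and N = 113 may change at the planned re-estimation.

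**A reader might infer that the primary outcome is untouched** because its model fixes the pre-session score. The rule is worded for all analyses, so it can add or drop further covariates there too. The size of that effect was not calculated.

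**Conclusion.** The concern holds. Neither secondary model names a covariate, valid pre-randomization data exist, and their only route in depends on chance balance. The firmest consequence is for type I error: at N = 113, about 5.2% to 6.3% as printed with one prognostic baseline (r = 0.3 to 0.6), and about 6% to 8% with four correlated ones (r = 0.3 to 0.5). Reversed, it is about 3.6% to 4.8%, and near nominal with several baselines.

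The power cost is less certain. With one baseline and log-SD 0.7 it is about 2 to 12 points as printed and 1.5 to 8 points reversed; with several correlated baselines it can be nil. For nurse pain it is small at SD 1.5. All these figures assume normal covariates and a single test per trial.

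A reader might go further and infer that the secondary results would be systematically biased. They would not be: randomization protects the comparison on average, and the 8% to 18% error rates apply only to the 11% of trials with large chance imbalance.

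**What to change.** 1. **Opioid model:** always include log(day-of-surgery PACU + ward MME + 1).
2. **Nurse-pain model:** always include one named pain score taken before randomization or before exposure. The first pre-intervention NRS is a good candidate: it should be available for every treated patient, precedes any session, and is less exposed to residual spinal block than day-of-surgery pain. Use it as a covariate only, since the outcome is limited to routine nurse scores.
3. **Section 3.F, all analyses including the primary:** replace the balance-triggered rule. Report standardized differences descriptively and name any further covariates in advance. Correcting the inequality alone is not enough.

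The cost is wording and one degree of freedom per model, with no new data. The change should be made before any unblinded analysis.

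One caution on the log transformation. It is undefined for a zero opioid total, but that should not be met by making patients with non-zero totals the main analysis. Section 3.F excludes only treated-set failures, those who did not "receive any treatment at all either due to refusal or because they chose to withdraw", and a zero total is a post-randomization outcome that the intervention may change. As an illustration, take a latent log-normal total with SD 0.7, a true 25% reduction and zeros below a threshold. Then 5% zeros in the control arm imply 11% under VR, and the reduction among non-zero patients shrinks to 19.5%.

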6. **Patient mobility score.** We will assess the effect of VR on patient mobility scores(s) during the postoperative day one (POD1), and until end of postoperative day 2 or hospital discharge, whichever occurs first, using a Wilcoxon rank-sum test, and report the median difference (along with the 95% CI) estimated using the Hodges-Lehmann approach.

Interim analyses. We will use a group sequential design to conduct interim analyses at each 25% of the planned enrollment to assess efficacy and futility of the intervention using a gamma spending function. Specifically, we will maintain the overall alpha level (monitoring efficacy) at 0.05 using gamma parameter of -4 [similar to O'Brien Fleming], and power at 90% (monitoring beta, type II error) using gamma parameter of -1 [more aggressive]. Under the alternative hypothesis (assuming a true difference of 1 point) the cumulative probability of crossing an efficacy (and futility in parentheses) boundary at the 1st through 4th analyses will be 0.08 (0.017), 0.36 (0.038), 0.71 (0.065) and 0.90 (0.10).

Sample Size Considerations. We base the sample size to have 90% power at the 0.05 significance level to detect a difference of 1 point or more between VR and placebo on the serial post-intervention NRS measurements in our linear mixed effects model. If we

Virtual Reality Distraction for Reduction in Acute Postoperative Pain

assume a SD of 1.5 points (taking into account the within-subject correlation in the repeated measures design), a total of 98 patients (49 per group) would be needed, and after adjusting for interim analyses, a total of 113. This sample size will also be sufficient for detecting moderate effect sizes in most of the other outcome variables.

Interim Pilot Study to Re-Assess variability.

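### The tertiary rank-sum analyses do not match the data and rules set out elsewhere in the plan: no single mobility value per patient is named, the anti-emetic effect estimate may be an uninformative 0, and the promised baseline adjustment cannot be made

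*Combined protocol and SAP*

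**What the plan says.** Mobility (section 3.E, Tertiary Outcomes 2): "We will measure patient mobility using physical therapy daily postoperative assessment", from the first pre-intervention pain score on POD1 to the end of POD2 or discharge. The analysis text (section 3.F, Tertiary Outcomes 6) reads "We will assess the effect of VR on patient mobility scores(s) during the postoperative day one (POD1), and until end of postoperative day 2" or discharge, with a Wilcoxon rank-sum test and a Hodges-Lehmann median difference. It does not say which day's score, or what summary of the two days, enters the test.

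Anti-emetics (section 3.E, Tertiary Outcomes 1): "the outcome variable will be calculated as the number of anti-emetic medications administered". Section 3.F, Tertiary Outcomes 5, refers to "the number of times a patient required anti-emetic medication" and uses the same test and estimator. Neither section gives an expected rate of use.

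Adjustment (section 3.F, opening paragraph): "For all analyses we will adjust for baseline variables having absolute standardized difference" meeting its threshold.

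Elsewhere in section 3.F, the routine nurse pain scores, which are also repeated, get a linear mixed model that accounts for within-subject correlation. System usability is analysed "using a Wilcoxon rank-sum test and report the median difference (along with the 95% CI) estimated using the Hodges-Lehmann approach", and the post-discharge score is treated in the same way.

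**The concern.** A two-sample rank-sum test compares two sets of independent values, one per patient. Mobility can supply one or two correlated values per patient, because the window spans two days and ends at discharge, and eligibility requires only one anticipated night. If the value is not fixed in advance, the analyst must either choose a day or summary after seeing data, or enter all scores and understate the variance.

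For a sparse count, the Hodges-Lehmann estimate (the median of all between-arm pairwise differences) can be exactly 0 even when the arms truly differ. A report of a significant P value beside a median difference of 0 would tell the reader nothing about the size of the effect.

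The adjustment rule covers all analyses, yet the named test takes no covariates. At stake are the two exploratory hypotheses in section 2 (mobility, and need for nausea and vomiting treatment).

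**Working it through.** **Inputs.** Group size comes from the sample-size paragraph of section 3.F. The plan's figure reproduces: 2 × (1.960 + 1.282)² × 1.5² / 1² = 47.3, so 48 per arm by the normal approximation; the t-based calculation gives 49 per arm (98 in total, power 0.904). Inflation for the stated spending functions is 1.132, giving 111 against the stated 113, which is close. 113 / 2 is about 56 per arm. The plan gives no figure for the tertiary outcomes, so the within-patient correlation, the share of patients with a POD2 score and the rate of anti-emetic use are all assumptions, shown as ranges.

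**1. Mobility, if both days were pooled as independent.** With within-patient correlation ρ:
- All patients have two scores: true variance / assumed variance = 1 + ρ.
- Half have two scores: (0.5 × 1 + 0.5 × (2 + 2ρ)) / 1.5 = 1 + ρ/1.5.
- Type I error = 2 × [1 − Φ(1.96 / √ratio)].

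| ρ | all with two scores | half with two scores |
|---|---|---|
| 0.5 | ratio 1.50, 11.0% | ratio 1.33, 9.0% |
| 0.8 | ratio 1.80, 14.4% | ratio 1.53, 11.3% |

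Simulation of the rank-sum test over the same settings gave 8.5-14.6%. Over wider assumptions (ρ 0.3-0.9, 25-100% with a POD2 score) it gave 5.9-14.6%. With one mean score per patient it gave 4.3-5.4%.

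**2. Anti-emetics.** The Hodges-Lehmann estimate is 0 when fewer than half of the pairwise differences are positive and fewer than half are negative. Let the control arm have any-use probability a and the VR arm b, and let users have 1 + Poisson(0.5) doses (mean 1.5). Two users then tie with probability 0.466, so one exceeds the other with probability (1 − 0.466)/2 = 0.267. The chance that a control patient's count exceeds a VR patient's is a(1 − b) + 0.267ab.

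| Any use, control vs VR | chance control exceeds VR | trials with estimate 0 | trials with estimate 0 and P<0.05 |
|---|---|---|---|
| 30% vs 15% | 0.267 | 100% | 48-49% |
| 40% vs 20% | 0.341 | 99% | 63% |
| 50% vs 30% | 0.390 | 97% | 52-54% |
| 60% vs 30% | 0.468 | 67-72% | 59% |
| 70% vs 35% | 0.520 | 37-38% | 31% |
| 80% vs 40% | 0.565 | 12-13% | 10% |

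The last two columns are simulated with 56 per arm; ranges are across repeat runs. The estimate leaves 0 as the third quantity, the chance of exceeding, passes one half. With heavier use among users (mean 2.5 doses) the share at 0 is 99% at 40% vs 20%, 57% at 60% vs 30%, 23% at 70% vs 35% and 4% at 80% vs 40%. Where control use is 15-30% and VR halves it, the 95% CI is exactly [0, 0] in 98-100% of trials. The rank-sum test itself still responds: power is about 49% at 30% vs 15% and 63% at 40% vs 20%.

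**3. Adjustment.** This needs no arithmetic. The opening rule of section 3.F covers all analyses; the test named for both tertiary outcomes, and for usability and the post-discharge score, has no place for a covariate.

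**The case against.** A reader might infer that the plan tests daily mobility scores as if they were independent. It does not say so. The wording leaves the variable open, and since the same plan handles repeated pain scores with mixed models, one value per patient is at least as plausible a reading. The inflated type I error belongs only to the pooled reading. What stands is that the analysis variable is undefined.

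A reader might also infer that the anti-emetic effect will almost always be estimated as 0. That requires mostly zero counts, and the documents give no rate. The line "Clinicians will be encouraged to give a single dose of dexamethasone (4-8 mg) for PONV prophylaxis" makes low later use plausible but supplies no figure. At high use with a large effect the estimate is usually not 0.

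Nor does the anti-emetic test fail. With one count per patient the tie-corrected rank-sum P value is valid; only the accompanying estimate and interval may be uninformative. The two descriptions of the count, medications administered and times required, can both be read as administrations, so that is loose drafting rather than a contradiction.

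Finally, the adjustment conflict is not peculiar to the tertiary outcomes. That is correct, and it widens the point rather than removing it.

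**Conclusion.** The point holds in three limited parts.

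- **Mobility:** the value entering the test is unspecified for patients with two scores. The cost is about 9-15% type I error if both days were pooled (assumed correlation 0.5-0.8, half or all patients with two scores), and otherwise a choice left open until data are seen.
- **Anti-emetics:** the test is sound, but the planned effect measure is at risk. It would be 0 in 97-100% of trials if use is no higher than about 50% vs 30%, and much less often at high use with a large effect. This depends on rates that the documents do not give.
- **Adjustment:** the rule and the named test are incompatible as written, with no assumption needed.

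The documents do not support saying that the analyses are invalid as a whole. Both outcomes are exploratory and the primary conclusion is untouched, so this is a minor improvement.

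**What to change.** Mobility: use a mixed model with day, arm and a patient random intercept, in line with the mixed model already planned for nurse pain scores. Alternatively, keep the rank-sum test on one prespecified value per patient and state that it is unadjusted.

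Anti-emetics: define the count as administrations in both sections. Report the proportion of patients with any use in each arm and the difference with its 95% CI, plus a rate ratio from a log-link count model with robust standard errors that carries the planned baseline adjustment.

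Wherever a rank-sum test is kept, including for usability and the post-discharge score, say that it is unadjusted and limit the all-analyses sentence accordingly.

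Cost: SAP wording and slightly more modelling, on the same data and with no change in design.

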We plan to re-estimate the sample size at the first interim analysis. For the outcome, the variance (σ^2) and ICC (ρ) will be estimated from the enrolled patients. Further, the correlation coefficient (r) between pre-intervention and post-intervention pain scores was also estimated. The variance for the outcome (σ^2) will be estimated for each of the pain score measurements separately and the most conservative (i.e., highest variance) option will be selected. Correlation coefficient was calculated in a similar manner and the lowest one was selected. For estimating ICC (ρ) a linear mixed effects model will be set up. We'll obtain estimates of between subject variance (σ_b^2) and total variance (σ_t^2) from the model and estimated ICC as σ_b^2/σ_t^2 .

Such a re-assessment “nuisance” parameters, does not affect the statistical properties of the design (i.e, does not increase type I error or decrease power). Keeping everything else the same as initially planned (90% power at the 0.05 significance level to detect a difference (Δ) of 1 point or more, 4 total analyses), we will calculate the new sample size using the equation below^{17,18}, where n is the number of observations required per group and m is the average cluster size. The total variance will be estimated by calculated by estimating the total variance for each observation separately and selecting the most conservative (i.e., highest variance) option. Correlation coefficient will be calculated in a similar manner. The number of patients required per group (N) would then be n/m .

$$n = \frac{(Z_{1-\alpha/2} + Z_{1-\beta})^2 2\sigma^2}{\Delta^2} \times (1 - r^2) \times (1 + (m - 1)\rho)$$

Virtual Reality Distraction for Reduction in Acute Postoperative Pain

If an increase in the total sample size is deemed necessary, the primary analysis will be carried out using the efficacy/futility boundaries for the new sample size.

Virtual Reality Distraction for Reduction in Acute Postoperative Pain

Addendum.

A. Pain Outcomes Questionnaire Short Form¹⁴ (POQ-SF)

01. On a scale of 0 to 10, with 0 being no pain at all and 10 being the worst possible pain, how would you rate your pain on AVERAGE on the LAST WEEK?

← 0 1 2 3 4 5 6 7 8 9 10 →
No pain Worst possible pain

02. Does pain interfere with your ability to walk?

← 0 1 2 3 4 5 6 7 8 9 10 →
Not at all All the time

03. Does your pain interfere with your ability to carry/handle everyday objects such as a bag of groceries or books?

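### The sample size re-estimation equation leaves out the interim-analysis inflation that took the planned total from 98 to 113

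*Combined protocol and SAP*

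**What the plan says.** All of this is in section 3.F (Data Analysis) of the combined protocol and SAP.

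- *Sample Size Considerations.* For a 1-point difference, an SD of 1.5 (within-subject correlation already allowed for), 90% power and alpha 0.05: "a total of 98 patients (49 per group) would be needed, and after adjusting for interim analyses, a total of 113".
- *Interim analyses.* There are looks at each 25% of planned enrollment. Efficacy uses gamma spending with parameter -4. Futility is set to hold "power at 90% (monitoring beta, type II error) using gamma parameter of -1". Cumulative crossing probabilities under a 1-point difference are printed for all four looks.
- *Interim Pilot Study to Re-Assess variability.* The design features are carried over: "of 1 point or more, 4 total analyses), we will calculate the new sample size using the equation below". The equation multiplies the fixed-design two-sample formula by (1 - r²) and by the design effect 1 + (m - 1)ρ. It is followed by "The number of patients required per group (N) would then be n/m". The variance input is chosen by "selecting the most conservative (i.e., highest variance) option", and the correlation by taking the lowest estimate. The section says the re-assessment "does not affect the statistical properties of the design (i.e, does not increase type I error or decrease power". It closes: "If an increase in the total sample size is deemed necessary, the primary analysis will be carried out using the efficacy/futility boundaries", meaning those that belong to the revised N.

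**The concern.** The first sizing has a fixed-design step and an interim-adjustment step. The re-estimation states only the first, yet treats its result as the new sample size and the patients required per group. The four-look boundaries still govern the resized trial, so the reason for the adjustment has not gone away.

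Two things are at stake. For given inputs, the rule misses the 90% it says it keeps. The section also names no reference N for deciding that an increase is needed. The natural reference is 113, the only interim-adjusted total in the document, and setting an uninflated 2(n/m) against it compares two different quantities. The omission acts only when variability is higher than planned, which is the case re-estimation exists to handle.

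**Working it through.** **Inputs from the plan.** Difference Δ = 1; SD 1.5; power 90%; alpha 0.05 (taken as two-sided, run as one-sided 0.025); 1:1 allocation; four equally spaced looks; gamma -4 for alpha and -1 for beta; totals 98 and 113.

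**Step 1: reproduce 98.** The two-sample t-test has 89.8% power at 48 per group and 90.4% at 49. So 49 per group, 98 in total, is reproduced.

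**Step 2: reproduce the interim design.** Cumulative spending at information fraction t is α(1 - e^(-γt))/(1 - e^(-γ)), and likewise for β. At t = 0.25 the beta spent is 0.10 × (1 - e^0.25)/(1 - e^1) = 0.10 × 0.2840/1.7183 = 0.0165. Numerical integration with non-binding futility gives upper bounds 3.155, 2.818, 2.439 and 2.014.

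| Under a 1-point difference | Look 1 | Look 2 | Look 3 | Look 4 |
|---|---|---|---|---|
| Efficacy, plan | 0.08 | 0.36 | 0.71 | 0.90 |
| Efficacy, recomputed | 0.076 | 0.359 | 0.712 | 0.900 |
| Futility, plan | 0.017 | 0.038 | 0.065 | 0.10 |
| Futility, recomputed | 0.0165 | 0.038 | 0.065 | 0.100 |

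The match identifies the planned design. Binding futility gives efficacy 0.071, 0.342 and 0.695 at the first three looks, which does not match.

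**Step 3: inflation factor.** The required drift is 3.4453, against 3.2415 for a fixed design: (3.4453/3.2415)² = 1.130. Then 98 × 1.130 = 110.7, close to the stated 113. The plan's own ratio is 113/98 = 1.153.

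**Step 4: what the re-estimation equation returns.** Let the effective variance per patient be σₑ² = σ²(1 - r²)(1 + (m - 1)ρ)/m. Then total N = 2(n/m) = 4 × 3.2415² × σₑ²/Δ² = 42.03 σₑ². At σₑ = 1.5 this is 94.6 (48 per group, 96 in total). That is the pre-adjustment figure on a normal-quantile scale, slightly below the t-based 98, and not 113.

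**Step 5: power of that N in the four-look design, inputs equal to the true values.** Drift is 3.2415. Power is 86.3% if the non-binding futility boundaries are followed and 89.4% if they are ignored. Treating futility as binding gives 87.6%.

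**Step 6: comparison with 113.**

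| | Scaled from 98 | z-formula |
|---|---|---|
| 113 looks sufficient up to σₑ, no factor | 1.5√(113/98) = 1.611 | √(113/42.03) = 1.640 |
| 113 is sufficient up to σₑ, factor 1.153 | 1.500 | 1.527 |
| 113 is sufficient up to σₑ, factor 1.130 | 1.515 | 1.543 |

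Where 2(n/m) just equals 113, the four-look design needs 113 × 1.130 = 128 to 113 × 1.153 = 130 patients.

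**Step 7: how far conservative inputs offset this.** If the inputs overstate the effective variance by 0%, 5%, 10%, 13% or 20%, power is 86.3%, 87.8%, 89.2%, 90.0% or 91.6%. Break-even is 13% on the variance, or √1.1297 - 1 = 6.3% on the SD.

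The whole rule was simulated with a floor of 113. The ICC and r values are assumptions, because the document gives none: ICC 0.3 to 0.7 and r 0.5 to 0.8. Also assumed were 28 patients at the interim (25% of 113), six sessions, normal scores, compound symmetry, equal true variances, all or half of patients present on day 2, and true effective SD 1.5, 1.64 or 1.9. Average power was 93-98% as written and 95-99% with the factor.

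**The case against.** The section says everything else stays as initially planned and lists four analyses. A sympathetic reader can take the equation as replacing only the fixed-design step, with the same adjustment to follow. That may be the intent. But the equation's output is called the new sample size, and n/m the patients required. A pre-specified rule should not rely on the reader to supply a 13-15% factor that the original sizing stated openly.

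The stronger objection is that 86% describes inputs the plan does not use. Taking the highest variance and lowest correlation over sessions from about 28 patients overstates the effective variance, usually by more than 13%. In a check under similar assumed values, with all sessions complete, the inputs passed break-even in 83-95% of simulated trials. This largely stands. It is why the point concerns a rule that does not secure its own target, and not expected power. The offset is not certain, and the plan does not present these inputs as a substitute for the interim adjustment.

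A reader might infer that the sentence denying any loss of power is false. The documents do not support that: they provide only for an increase, so power is not lowered relative to a 113-patient trial. The sentence simply does not guarantee 90%.

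**Conclusion.** The point holds as a defect in the stated rule. For given inputs the equation asks for 11.5% fewer patients than the recomputed factor requires (1 - 1/1.130), or 13.3% fewer on the plan's own ratio (1 - 98/113). With accurate inputs its N has 86-89% power, the range depending on whether futility crossings are obeyed. The exposed range of effective SD runs from about 1.5 to about 1.61-1.64.

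It would be tempting to conclude that the trial is underpowered. That is not shown. Nothing changes at SD 1.5, and average power of the whole rule stays above 90% in every assumed scenario. Type I error is unaffected by the omission, because the boundaries are set for the new sample size. Nor are 98 and 113 wrong: the first reproduces exactly and the second closely.

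The result assumes alpha 0.05 two-sided, equally spaced looks, and non-binding futility, which the printed crossing probabilities support. The change should be made; it is not critical.

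**What to change.** 1. State that maximum total N = 2(n/m) × the group-sequential inflation factor for the planned four-look design, taken from the design software or as 113/98.
2. Compute it on the same scale as the original 98. The z-formula gives 94.6 at SD 1.5, so the factor alone returns 94.6 × 1.130 = 107 or 94.6 × 1.153 = 109, not 113. A t-based calculation, or rescaling by 98/94.6, removes the mismatch.
3. Name 113 as the reference and the floor, so that N can only increase.
4. Reword the sentence on power: 90% is met when N includes this factor and the nuisance estimates are accurate.

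If the larger N is not wanted, either state that the uninflated N gives 86-89% power for accurate inputs, or say that the conservative inputs are intended to cover the interim adjustment.

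The cost is one factor, one comparison rule and one sentence. For given inputs the re-estimated N is 13-15% larger whenever an increase is triggered. No patients are added if the re-estimated effective SD is 1.50 or less (up to about 1.54, depending on scale and factor).
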